## 2 CLINICAL INVESTIGATION SYNOPSIS

Investigation title	Intracochlear potentials: Intraoperative measurement clinical investigation.
Investigation number	CLTD5663
Short investigation title	Volta  study.
Name of investigational devices	Unapproved intraoperative Surgical Assistant Research Tool (SA16) software. Approved Nucleus Freedom Sound Processor, Freedom POD, Nucleus 6 CP900 Series Sound Processor, CR220 Intraoperative Remote and accessories.
Investigation start (Mmm yyyy)	March 2017
Total expected duration of the clinical investigation	Twelve months
Enrolment period	12 months
Expected duration per subject	Single visit (surgery)
Investigational design	Prospective, non-randomized, single arm feasibility clinical investigation with sequential enrollment.
Number of subjects	20
Inclusion criteria	
 
1. Meet current cochlear implant indications at the implanting centre for a CI512, CI422, CI522 or CI532 cochlear implant
 
2. Aged 18 years and older at the time of implantation.
 

Exclusion criteria	
 
1. Recipient of a Nucleus 24 ABI device
 
2. Medical or psychological conditions that contraindicate undergoing general anaesthesia or surgery.
 
3. Ossification, malformation or any other cochlear anomaly, such as common cavity, that might prevent complete insertion of the electrode array, as confirmed by medical examination.
 
4. Unwillingness or inability of the candidate to comply with all investigational requirements.
 

Primary objectives	Collection of normative voltage tomography data during and/or immediately after electrode insertion into the cochlea using SA16 research software.

Investigation schedule	Procedure	Pre-op	Surgery			
	Consent	x				
	Medical History	x				
	Voltage tomography		x			
	AE, ADE, DD		x			
	X-Ray		(x)			
	Data file		x			
Primary endpoints	Report on normative voltage tomography data for CI512, CI422, CI522 or CI532 cochlear implant recorded with SA16 research software during and/or immediately after electrode insertion.					

### 3 IDENTIFICATION AND DESCRIPTION OF THE INVESTIGATIONAL DEVICE

The Surgical Assistant Research Tool (SA16) research software is a software tool developed by Cochlear Limited. The use of the SA16 research software in the current clinical investigation is intended to support Cochlear's research into the development of implant telemetry based surgical tools.

The SA16 research software is designed to perform a series of predefined measurements with minimal intervention both during and immediately following electrode insertion using telemetry from the implant via the Sound Processor to the PC. These measurements include real time continuous measurements, intended for use during the electrode insertion portion of the surgical procedure, and baseline measurements following the completion of electrode insertion, as detailed in Figure 1.

[figure not shown]

Figure 1: SA16 software usage flow.

---

The SA16 research software is intended for use in the intra-operative condition, with patients under a general anaesthetic only. The SA16 research software is designed to work with cochlear implants which:

1. Incorporate a fourth generation cochlear neural stimulator integrated circuit
  - i. E.g. Freedom, CI400 & CI500 Series implants
2. A minimum electrode pad size of 0.0248 mm^2
  - i. Note that all Freedom, CI400 and CI500 series implants (Up to and including CI422, CI522 & CI532) have a guaranteed minimum electrode pad size of at least 0.1mm^2
3. Have 22 electrodes intended for intra-cochlear placement.

The SA16 research software is designed to work with the following hardware:

[figure not shown]
1. Nucleus Sound Processors and Nucleus 24 coils (excluding the 2m intra-operative coil)
  - i. Freedom, CP810 and CP900 Series Sound Processors
2. Personal Computer (PC) or tablet with EN 60950 UL compliance and the MS Windows® 10 operating system.
3. Freedom Programming POD and USB cable
4. Freedom Programming Cable (Z60780) and Programming Shoe (Z60765), CP800/CP900 Programming Shoe and Cable (Z195607)

The SA16 research software will be used in the current clinical investigation in adults who meet current indications for cochlear implantation in Australia. The SA16 research software is not for use with patients who are receiving an implant that directly contacts neural tissue, such as auditory brainstem implants (ABI).

SA16 research software is a device which is not yet commercially available for any purpose. The device will be provided preinstalled on a dedicated PC and POD optimised for use with SA16 by Cochlear Limited. Traceability will be maintained by the Clinical Project Manager.

The external envelope materials of the Nucleus CI512, CI422, CI522 or CI532 cochlear implants, and sterile accessories (coil and cables), and the Nucleus Sound Processors are in biocompatible according to applicable standards (i.e. ISO 10993: 2009/AC: 2010).

All equipment that enters the sterile field, including the programming cable, Sound Processor and coil will be placed in a sterile bag or sleeve by a member of the operating room staff who is dressed and qualified to work inside the sterile field.

**Figure 2: Equipment setup for SA16**

In the current clinical investigation only clinicians who have received the necessary training and experience needed to use the SA16 research software will be permitted to collect voltage tomography data.

Other than the recording of normative voltage tomography data during and/or after electrode insertion into the cochlea with the SA16 research software, no other specific medical or surgical procedures are envisaged in the clinical investigation.

This clinical investigation will gather voltage tomography data for retrospective analysis by Cochlear Limited. No real time feedback will be provided to the surgeon during the surgery.

As an alternative to the use of SA16 research software intraoperatively, a future unapproved version of Custom Sound EP software may be used to make voltage measurements..

## **4 JUSTIFICATION FOR THE DESIGN OF THE CLINICAL INVESTIGATION**

The clinical investigation will gather impedance and transimpedance (voltage tomography) data intra-operatively which can be used to characterise the electrical properties of the living cochlea. Outcomes from the clinical investigation will provide normative voltage tomography data during and/or after electrode insertion into the cochlea.

Experiments in computer models, artificial cochleae and temporal bones have shown that electrical measures can be made that may provide information on the position of the electrode array in the cochlea (1, 2). A combination of impedance and transimpedance (voltage tomography) measurements may be used to infer:

- Angular depth of insertion
- Proximity to the modiolus
- Presence of electrode tip fold-over
- Changes in these parameters over time

The current clinical investigation is designed as a prospective, non-randomised, single arm feasibility clinical investigation with sequential enrollment. The clinical investigation will measure impedance and voltage tomography during twenty cochlear implant surgeries to determine the relevant data signatures and to understand normal variability in voltage tomography due to anatomy and other factors.

A summary of the relevant pre-clinical assessment and/or clinical data is provided in the Intracochlear Potentials Investigators Brochure (IB) (3).

## **5 RISKS AND BENEFITS OF THE INVESTIGATIONAL DEVICE AND CLINICAL INVESTIGATION**

### **5.1 Clinical Benefits**

There are no anticipated clinical benefits for the patient through participation in the clinical investigation. The outcomes from the clinical investigation will be used by Cochlear Limited to support development of implant telemetry based surgical tools.

### **5.2 Anticipated adverse device effects.**

Participants in the clinical investigation are exposed to the anticipated adverse device, and or procedure related effects associated with standard cochlear implant surgery, general anaesthesia and intraoperative Neural Response Telemetry (NRT).

The risks to the participant introduced with the use of SA16 research software are comparable to standard cochlear implant surgery are described within the Investigators Brochure (IB) (3).

Interactions with concomitant medical treatments are not envisaged in the use of SA16 research software during the clinical investigation.

### **5.3 Residual risks**

Residual risks related to the use of the investigational device have been reduced to as low as reasonably possible and are described in the Hazards Analysis (6).

### **5.4 Risks associated with participation in the clinical investigation**

Participants in the clinical investigation are exposed to the anticipated adverse device, and or procedure related effects associated with standard cochlear implant surgery, general anaesthesia and intraoperative Neural Response Telemetry (NRT). The risks to the participant introduced with the use of SA16 research software are comparable to standard cochlear implant surgery are described within the Investigators Brochure (IB) (3).

---

Interactions with concomitant medical treatments are not envisaged in the use of SA16 research software during the clinical investigation.

## 5.5 Risk mitigations

Mitigation of identified risks associated in the use of the SA16 research software are described within the Investigators Brochure (IB) (3).

## 5.6 Risk-to-benefit rationale

The identified risks associated with the use of SA16 research software in this clinical investigation have been mitigated to ensure the incremental risk associated with its use are as low as reasonably possible (6).

Therefore, the risk benefit ratio of participating in this clinical investigation is similar to the risk benefit ratio of undergoing conventional cochlear implant surgery and intraoperative NRT measurements.

# 6 OBJECTIVES AND HYPOTHESES

## 6.1 Objectives

### 6.1.1 Primary objective

The primary objective of the clinical investigation is collection of normative voltage tomography data during and/or immediately after electrode insertion into the cochlea using Surgical Assistant Research Tool (SA16) software.

## 6.2 Hypotheses

As this feasibility clinical investigation aims to collect normative voltage tomography data for the development of implant telemetry based surgical tools, there are no formal hypotheses to be accepted or rejected by statistical data from the clinical investigation.

## 6.3 Claims and intended performance

The claims and intended performance of SA16 research software that are to be verified during the clinical investigation are:

1. Measurement of voltage tomography during and/or immediately after electrode insertion to provide a baseline measurement for the CI512, CI522, CI422 and CI532 cochlear implants.

## 6.4 The risks and anticipated adverse device effects

There are no risks or anticipated adverse device effects that are to be assessed in the clinical investigation.

## 7 DESIGN OF THE CLINICAL INVESTIGATION

### 7.1 General

The current clinical investigation is designed as a prospective, non-randomized, single arm feasibility clinical investigation with sequential enrollment. The purpose of the clinical investigation is to gather normative voltage tomography data with the SA16 research software. No real time feedback will be provided to the surgeon during surgery.

A single-subject repeated-measures analysis will be employed whereby subjects will act as their own control. A single-subject research design is appropriate since it accommodates the heterogeneity that characterizes hearing-impaired populations. Blinding procedures are not appropriate for this clinical investigation design, as it is not possible to conceal the presence, or absence, of the investigational devices from the investigators.

### 7.2 Endpoints

#### 7.2.1 Primary endpoint

The cochlear implant surgery visit serves as the primary endpoint for data collection related to normative voltage tomography data during electrode insertion and/or immediately post-insertion for CI512, CI422, CI522 or CI532 cochlear implants as recorded using SA16 research software.

### 7.3 Equipment

The following equipment will be used for assessment of electrode impedance and transimpedance (voltage tomography):

- A computer (laptop or tablet) with custom designed Cochlear Ltd software installed.
- Programming controller interface (to provide electrical isolation for the participant), Sound Processor (Freedom or CP900) and associated transmitting coil and cabling.

### 7.4 Visit Schedule

Procedure	Pre-op	Surgery			
Consent	x				
Medical History	x				
Voltage tomography		x			
AE, ADE, DD		x			
X-Ray		(x)			
Anonymized data file		x			

## 7.5 Investigational device and comparator

The investigational device for assessment of electrode impedance and voltage tomography in the clinical investigation is the Surgical Assistant Research Tool (SA16) research software. SA16 is an unapproved software tool developed by Cochlear Limited, intended to support research into the development of implant telemetry based surgical tools.

The SA16 research software is designed to perform a series of predefined impedance and voltage measurements with minimal intervention during and immediately following electrode insertion. The recordings made by SA16 software will be analysed by Cochlear Limited to provide a baseline measurement for the CI512, CI522, CI422 and CI532 cochlear implants. If an electrode tip fold-over is identified on intraoperative or post-operative X-ray, after surgery, the SA16 recordings will be analysed to further develop the underlying algorithm.

CS19 (1.6.2) software is approved for use in Australia by Cochlear staff members. Electrical impedances and Evoked Compound Action Potentials (ECAP) may be collected intraoperatively with the Nucleus 6 CR220 Remote or Custom Sound EP.

As an alternative to the use of SA16 research software intraoperatively, a future unapproved version of Custom Sound EP software may be used to make intraoperative voltage tomography measurements.

The use of a comparator device is not envisaged in this clinical investigation.

No other medical devices or medications are specified for use during the clinical investigation.

## 7.6 Subjects

The eligibility criteria for participation in the clinical investigation are described below.

### 7.6.1 Inclusion criteria

1. Meet current cochlear implant indications at the implanting centre for a CI512, CI422, CI522 or CI532 cochlear implant
2. Aged 18 years and older at the time of implantation.

### 7.6.2 Exclusion Criteria

1. Recipient of a Nucleus 24 ABI device
2. Medical or psychological conditions that contraindicate undergoing general anaesthesia or surgery.
3. Ossification, malformation or any other cochlear anomaly, such as common cavity, that might prevent complete insertion of the electrode array, as confirmed by medical examination.
4. Unwillingness or inability of the candidate to comply with all investigational requirements.

### **7.6.3 Subject withdrawal**

Any subject may voluntarily discontinue the study at any time without prejudice. The Investigator may discontinue a subject from the study at any time if (s)he considers that remaining in the study compromises the subject's health or the subject is not sufficiently cooperative. In either event, reason(s) for discontinuation should be recorded on a study withdrawal form, provided as part of the CRFs for the study. Possible reasons for study discontinuation include the following:

- AE necessitating discontinuation from the study
- The subject is lost to follow-up
- Voluntary decision to withdraw consent made by the subject
- Investigator decision
- Other reason

In case of a subject lost-to-follow-up, the Investigator must attempt to contact the subject (or relative/family contact) by phone, email or letter at least three times. If attempts are unsuccessful, the 'subject withdrawal' form is to be completed in the study file and reported, as appropriate, in required reports to the Sponsor, EC and TGA.

### **7.6.4 Point of enrolment**

Subjects are enrolled into the clinical investigation when they have signed the Patient Informed Consent form (PIC). The process of obtaining informed consent will be undertaken by the implanting surgeon.

### **7.6.5 Total expected duration of the clinical investigation**

The total expected duration of the clinical investigation is twelve months. The total duration will be dependent on the ability to recruit the required number of subjects within the enrolment period. The expected duration of each subject's participation is a single visit (during surgery).

### **7.6.6 Number of subjects required to be included in the clinical investigation**

The number of subjects required to be included in the clinical investigation is twenty. The estimated time needed to select this number (i.e. enrolment period) is twelve months.

---

 Withdrawal of consent is defined as the subject's voluntary decision to revoke consent to continue participation in the study.

 Subject withdrawal from the study is defined as an Investigator decision. The Investigator may elect to withdraw a subject from the study at any time if he/she considers that remaining in the study compromises the patient's health or if the Investigator considers the subject lost to follow-up.

## 7.7 Procedures

### 7.7.1 Surgery

The clinical investigation will gather data only. The clinical investigation will not attempt to process the data in real time or provide real time feedback to the surgeon during the surgery. Data gathering will be initiated and controlled by a Cochlear or HEARing CRC staff member not directly involved with the surgery at a time and in a manner as to minimise interference with the surgical procedure.

#### 7.7.1.1 Electrically evoked compound action potentials – ECAP

ECAP thresholds will be recorded using the AutoNRT algorithm in the Nucleus 6 CR220 Intra-operative Remote Assistant or Custom Sound EP software as per standard clinical protocols. AutoNRT will be performed on all electrodes prior to voltage tomography measurements with SA16.

#### 7.7.1.2 Voltage Tomography (SA16)

The following data collection with SA16 research software will occur during electrode insertion and/or immediately following electrode insertion:

- Stimulation and measurement using a variety of stimulation and recording configurations at 230 CL to characterise the electrical properties of the living cochlea during tissue integration of the electrode. Measurement time is approximately ten minutes.

The voltage tomography measurements following electrode insertion may be made after closure within theatre or in recovery.

The recordings made by SA16 software will be retrospectively analysed by Cochlear Limited to provide a normative measurement for the Nucleus CI512, CI422, CI522 or CI532 cochlear implant.

If an electrode tip fold-over is identified on X-ray, the SA16 recordings will be analysed by Cochlear Limited to further develop the underlying algorithm.

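### Section 3 confines SA16 to anaesthetised patients during surgery, but Section 7.7.1.2 lets the post-insertion recording be made in recovery with no anaesthetic condition

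*Protocol*

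**What the plan says.** Section 3, which describes the device, states: "The SA16 research software is intended for use in the intra-operative condition, with patients under a general anaesthetic only". The synopsis (Section 2) likewise lists the device as "Unapproved intraoperative Surgical Assistant Research Tool (SA16) software".

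Section 7.7.1.2 is the procedure for SA16 recordings. On timing it says: "The following data collection with SA16 research software will occur during electrode insertion and/or immediately following electrode insertion". The activity is "Stimulation and measurement using a variety of stimulation and recording configurations at 230 CL", and "Measurement time is approximately ten minutes". It then adds: "The voltage tomography measurements following electrode insertion may be made after closure within theatre or in recovery". No anaesthetic condition is attached, and no other level is given for a recording made in recovery.

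Section 7.7.1 assigns control of the recording to a staff member not directly involved in the operation, who is to act "at a time and in a manner as to minimise interference with the surgical procedure". Section 7.5 allows a substitute for SA16: "a future unapproved version of Custom Sound EP software may be used to make intraoperative voltage tomography measurements".

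**The concern.** The two sections give different rules for the same recording with the same software. Section 3 uses the word only, which leaves no room for exceptions. Section 7.7.1.2 then permits a setting that is not intra-operative on its face and in which patients commonly emerge from anaesthesia.

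The person controlling the recording works from Section 7.7. The anaesthetic condition is not repeated there, and the one timing instruction concerns interference with surgery. That instruction does not mention anaesthetic state and, if anything, gives a reason to record later. A recording in a waking patient would comply with the procedure and yet fall outside the stated condition of use of an unapproved device. Section 5.1 anticipates no clinical benefit for participants, so there is nothing on the benefit side to set against use outside that condition.

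**Working it through.** The plan has no figure to reproduce, and the point does not depend on sample size, power or error rates. The check is a comparison of the two rules, followed by a search for anything that reconciles them.

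**The two rules compared**

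| Item | Section 3 | Section 7.7.1.2 |
|---|---|---|
| Software | SA16 | SA16 |
| Setting | Intra-operative | Post-insertion recording in theatre after closure, or in recovery |
| Patient state | General anaesthetic only | Not stated |
| Level | Not stated | 230 CL, given once for all SA16 collection |

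**Which combinations satisfy both sections**

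- In theatre after closure, still anaesthetised: both are satisfied.
- In recovery, still anaesthetised: the anaesthetic limit is met, but the intra-operative limit is not met on its face.
- In recovery, waking or awake: Section 7.7.1.2 is satisfied and both limits in Section 3 are breached.

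The defect is therefore confined to the recovery option.

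**Search for a reconciling statement**

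- The visit schedule (Sections 2 and 7.4) places voltage tomography under surgery and does not mention anaesthetic state.
- The risk-benefit rationale (Section 5.6) compares participation with conventional implant surgery and intraoperative NRT. It does not mention recordings in recovery.
- The Custom Sound EP alternative (Sections 3 and 7.5) does not account for the recovery option. That option sits in the SA16 section, and Section 7.5 describes the alternative as being for intraoperative measurements too.
- Nothing in Section 7.7 cross-refers to the limit in Section 3, requires a check of anaesthetic state, or sets a reduced level.

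**Possible extent**

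Inputs: 20 subjects (Section 7.6.6) and about ten minutes of measurement per subject (Section 7.7.1.2). The share recorded in recovery is not given, so the shares between the two extremes are assumptions.

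Subjects = 20 × share; minutes = subjects × 10.

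| Share in recovery | Subjects | Measurement time |
|---|---|---|
| 0% | 0 | 0 min |
| 10% | 20 × 0.10 = 2 | about 20 min |
| 25% | 20 × 0.25 = 5 | about 50 min |
| 50% | 20 × 0.50 = 10 | about 100 min |
| 100% | 20 | about 200 min |

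The minutes are ceilings. The ten minutes is measurement time, not stimulation time. It is also stated once for collection during and/or after insertion, so not all of it need fall after insertion.

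**The case against.** The best defence is that the sections address different things: Section 3 fixes the patient's state, while Section 7.7.1.2 only permits a place. On that reading the anaesthetic limit carries over without being repeated. Section 11 forbids departures from the whole plan except in emergencies, so recording a waking patient would already be a deviation. Section 3 also restricts data collection to clinicians trained on SA16. This has some force on anaesthetic state. It does not remove the conflict over setting, because recovery is hard to call intra-operative. It also leaves the operator with an express permission in one section and an unreferenced prohibition in another. A strict rule on deviations makes it more important that the two agree.

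A second objection is that no harm is shown. That is right as far as it goes. The protocol does not explain the limit or say what 230 CL would mean for a waking recipient. The Investigator's Brochure and hazards analysis, to which it refers for risks, are not available here and may cover the point. They might explain the limit, but they could not make these two statements consistent.

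It is also fair to say that the minute counts are loose, that the synopsis wording, the Custom Sound EP text and the timing instruction are secondary support, and that a single added clause could resolve the anaesthetic part. None of this alters the contradiction.

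**Conclusion.** The concern holds. As written, Section 7.7.1.2 authorises a use of SA16 that Section 3 excludes, and nothing in the protocol reconciles them. This is a rule wrongly stated, not a detail left to another document. It should be corrected before recordings are made, because it concerns the condition of use of an unapproved device in subjects with no anticipated benefit.

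The extent cannot be fixed from the protocol; it lies anywhere between none and all 20 subjects. The conclusion rests on the plain meaning of intra-operative and on the absence of any anaesthetic requirement in Section 7.7. It does not rest on the assumed shares. No specific harm and no effect on the endpoint is claimed.

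**What to change.** Strike the recovery alternative (the last three words of the sentence) from Section 7.7.1.2, and state that post-insertion recordings are made in theatre, after closure if needed, while the patient remains under general anaesthetic.

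A lighter alternative is to keep recovery but require confirmed continuing general anaesthesia. Section 3 would then also need to say that recovery is an acceptable setting. If the sponsor wants recordings in patients who are no longer anaesthetised, Section 3 must be amended and the change supported by a risk assessment and stimulation limits for that state.

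It would also help to record the setting, the anaesthetic state and the time since full insertion for each recording, if the case report form does not already do so. The normative report could then describe the conditions of measurement. This is optional.

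The cost is a wording amendment and up to three recorded items, with no extra patients or procedures. The price is some scheduling flexibility and possibly a few lost post-insertion recordings.
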